5.3 Study Drug Supplies

The Nucleus ABI24 system is already FDA-approved for use in NF2 patients. As with other cochlear and brainstem implants, the Nucleus ABI24 device is ordered prior to surgery. Notably, the Nucleus ABI24 device is already being used at MEEI in NF2 patients and standard preparation, dispensation, handling, and administration protocols are already in place. Similar protocols will be used in our study for the ABI541. In particular, upon receipt the device will be kept in storage with other electrical implant devices at MEEI, and at the time of surgery, dispensed/opened and subsequently handled with appropriate sterile technique. Thus, formulation and packaging, preparation and dispensation, and administration issues are either already addressed through current protocols or not applicable to our study.

5.4 Study Drug/Device-Storage and Accountability

The Nucleus ABI24-system~~541~~ is stored at room temperature upon receipt and kept securely until it is used during surgery. Given its electronic components, prolonged exposure to extreme temperatures should be avoided. In our study, the Nucleus ABI24-system~~541~~ will be kept in storage with other electrical implant devices at MEEI, and at the time of surgery, dispensed/opened and subsequently handled with appropriate sterile technique. Nearly all aspects of the device are implanted in the patient (with the exception of the speech processor and microphone/headset, which are worn externally). The device contains a few disposable components, which are primarily used to accurately place the device intra-operatively. These components will be disposed of in biological waste containers during the surgery. Because the ABI24-system~~541~~ is an implanted device, protocols for the proper destruction or disposition of study devices upon completion or termination of the clinical research are not necessary.

5.5 Other Medications

Our study does not include the planned use of other medications concomitantly with the Nucleus ABI24-system~~541~~ device. If patients experience complications or medical concerns related to the Nucleus ABI24-system~~541~~, these will be handled appropriately through routine medical management in the Otology clinic or appropriate referral to other providers. There are no specific medications that are not allowed in participants of our clinical research study. In addition, rescue medication or therapies will not be used in this study.

6. BIOSPECIMEN COLLECTION (IF APPLICABLE)

Biospecimens will not be collected as part of our study. Thus, specimen, preparation, handling, shipping and other aspects of specimen management are not applicable.

6.1 Specimen preparation, handling, and shipping

N/A

6.2 Instruction for specimen preparation, handling and storage

N/A

6.3 Specimen shipment

N/A

6.4 Future use of stored specimens

N/A

7. STUDY PROCEDURES

7.1 Screening Procedures

After confirming that potential study participants meet basic demographic inclusion criteria, patients will be evaluated by a trained Otologist at MEEI. A detailed history will be obtained and physical exam will be completed. Subjects will also be evaluated for baseline qualitative measures using questionnaires and quantitative

measures using audiologic testing. In particular, audiometric threshold testing and Auditory Evoked Potential testing will be completed to confirm acoustic auditory status. These parameters will be compared to inclusion criteria to determine if a subject meets all inclusion criteria and represents a viable candidate for ABI surgery.

7.2 Enrollment/Baseline Procedures

All baseline procedures will be completed at the time of screening. This includes qualitative measurement using the Modified Hearing Handicap Inventory, Dizziness Handicap Inventory, and Quality of Life (SF-36) questionnaires as well as audiologic tests such as standard audiometric threshold and Auditory Evoked Potential testing.

7.3 Study Drug or Device Procedures

Subjects will undergo pre-operative evaluation for ABI surgery. Those subjects that are appropriate for surgery will undergo a procedure for implantation of the ABI24 system⁵⁴¹. As per manufacturer protocol, the parameters of the ABI24 system⁵⁴¹-including adjustment of electrode sensitivities and activation of specific electrodes will be completed at each follow-up visit post-operatively. This process involves adjustment of device parameters by a trained audiologist who subsequently administers audiologic tests to confirm optimal activation of the ABI24 system⁵⁴¹.

7.4 Standard of Care Procedures

All audiologic testing and assessments represent the standard of care. Aspects of our study that go beyond routine standard of care are outlined above and in the informed consent.

7.5 Follow-up Procedures (Incorporate only if follow-up procedures will be performed)

Study participants will have audiologic testing and device activation and adjustment completed at follow-up appointments. These post-operative follow-up

appointments will occur at 4-12 weeks, three, six, and twelve months, and biannually thereafter until the study end point of five years. Timing of these appointments may vary by as much as four weeks prior to or after the planned follow-up date (e.g. between 2-4 months for the 3 month follow-up).

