3. STUDY DESIGN

3.1 Study Design Description

The study of the Nucleus ABI24 and ABI541 in non-NF2 patient will be conducted as a repeated-measure, single subject experiment with up to fifteen replications (goal of ten subjects, with 15 initially recruited to account for withdrawal or termination). A single subject research design in which each subject will serve as his or her own control will accommodate the heterogeneity of the subjects' background that is well known to influence auditory prosthesis outcomes and measures. Post-operative evaluations will be conducted at initial device activation, and three, six, and twelve months post-activation. Because the presence of absence of an ABI is easily recognized from visual inspection, blinding and masking procedures will not be utilized as part of the study design. The safety of the implant will be determined by monitoring major and minor complications in the cohort of study participants.

Pre-operative baseline measures will be obtained, including standard audiologic testing as described below.

Candidates that are suitable for surgery will undergo placement of an ABI. This surgery will utilize a translabyrinthine or retrosigmoid approach, depending on the anatomical and patient specific factors, to obtain access to the auditory nucleus of the brainstem. The electrode array of the ABI will then be placed and tested intra-operatively. After confirmation of optimal electrode array placement, the receiver will be implanted within the temporal bone posterior to the pinna. The patients overlying subcutaneous tissue and skin will then be closed and covered with dressings using standard surgical techniques.

Following surgical implantation of the Nucleus ~~ABI24~~ ABI541 and 4-12 weeks of healing, the device will be activated and auditory performance will be assessed as follows: at the time of activation and at three, six, and twelve months post-activation. Subjects will be evaluated with the prior approved Nucleus ~~ABI24~~ ABI541 speech processor programmed with an approved sound processing algorithm. Post-operative auditory function will be tested with a battery of psychophysical, speech perception, and lip-reading enhancement measurements.

The detailed list of post-operative assessments includes:

Initial Activation

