Approximately 4-12 weeks post-operatively, subjects will be fitted with an approved Nucleus Sound Processor and initial stimulation will take place. The following procedures will occur at this visit:

- Modified Hearing Handicap Inventory, Dizziness Handicap Inventory, and Quality of Life (SF-36) questionnaires will be administered (see attached)
- Detection measures
- Speech perception and lip-reading enhancement measures
- Psychophysical measures
- Safety measures

Three, Six, and Twelve Months, and Biannual Post-activation Visits (for five years following ABI surgery):

The following procedures will occur at all these visits unless otherwise specified:

- Modified Hearing Handicap Inventory, Dizziness Handicap Inventory, and Quality of Life (SF-36) questionnaires will be administered (see attached)
- Detection measures at each post-activation interval

- Speech perception and lip-reading enhancement measures at each post-activation interval
- Psychophysical measures at each post-activation interval
- Safety measures at each post-activation interval

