8. SAFETY AND EFFECTIVENESS ASSESSMENTS

8.1 Safety Assessments

Safety assessments will include complications questionnaires and frequent post-operative follow-up visits. Inquiries about both major and minor complications will be made and any complications will be recorded. A research assistant will regularly review safety measures every month for all study participants and discuss any safety concerns/adverse outcomes with the investigator.

Any reported safety issues will be carefully recorded and following completion of the study, safety outcomes will be analyzed. Any unanticipated adverse events will be reported to the HSC, FDA, and Cochlear Americas (see Section 9).

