8.2 Effectiveness Assessments

Effectiveness assessments will be completed based on audiologic testing and subjective questionnaires at each follow-up appointment. These will be compared to the subjects pre-operative baseline measures. In particular, primary dependent measures will include:

- Speech Perception and Lip-reading Enhancement Measures
 1. Monosyllable/Trochee/Spondee Test (MTS), presented via live voice
 2. CUNY Sentences, presented via video laserdisc in the sound-alone, vision alone, and sound-plus vision conditions

- Detection Measures
 3. Aided (ABI) Sound Field Thresholds measured at octave intervals from 250 to 6000 Hz inclusively.

- Psychophysical Measures
 4. Electrical Thresholds Measured in Current Level
 5. Electrical Maximum Comfort Levels Measure in Current Level
 6. Pitch scaling

- Subjective Questionnaires
 7. Hearing Handicap Inventory
 8. Dizziness Handicap Inventory
 9. Quality of Life (SF-36) questionnaire

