10. STATISTICAL METHODS/DATA ANALYSIS

10.1 Primary endpoint(s) or outcome measure (s)

The study has a primary endpoint of five years following ABI surgery for up to fifteen study participants. Outcomes measures include audiologic measures and subjective questionnaires as described in previous sections, as well as safety assessments completed throughout the study.

Our previous work has established the importance of these physiological, psychophysical, speech tests, questionnaires on efficacy, and safety measures as a comprehensive method for assessing the outcomes of ABI surgery in non-NF2 patients. In particular, using these measures we can obtain both objective and subjective data to assess the safety and efficacy of ABI placement in non-NF2 patients and thereby understand how ABI placement has influenced patients' hearing and quality of life. In addition, by comparing our findings and measures to data obtained in other patient populations such as NF2 patients, we will better understand whether ABI placement in non-NF2 patients has improved safety and efficacy compared to ABIs in other patient populations.

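### Do visits counted from activation miss interim and five-year dates counted from surgery?

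*Combined protocol and SAP*

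**What the plan says.** Section 3.1 sets the visit clock at activation: "Post-operative evaluations will be conducted at initial device activation, and three, six, and twelve months post-activation". It places activation itself relative to surgery: "Approximately 4-12 weeks post-operatively, subjects will be fitted with an approved Nucleus Sound Processor and initial stimulation will take place". The later visits carry both clocks in one heading: "Biannual Post-activation Visits (for five years following ABI surgery".

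Section 7.5 gives the same series as "appointments will occur at 4-12 weeks, three, six, and twelve months, and biannually thereafter until the study end point of five years". It calls these visits post-operative and attaches no origin to the individual times. It then allows a window: "Timing of these appointments may vary by as much as four weeks prior to or after the planned follow-up date".

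Under section 8.2 the hearing data come from these visits: "Effectiveness assessments will be completed based on audiologic testing and subjective questionnaires at each follow-up appointment".

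Section 10.1 states: "The study has a primary endpoint of five years following ABI surgery for up to fifteen study participants". Section 10.7 plans interims for cohorts of three, five and eight enrolled patients, at one and three years after the operation. It does not say which visit supplies the data or where the data are cut. The study grid (section 7.8) sits in the IRB application and is not part of the documents reviewed.

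**The concern.** Visits appear to run on one clock and analyses on another, with nothing linking them. If the 12-month visit is counted from activation and the one-year interim from surgery, the visit comes after the interim. A recently operated subject would then contribute only a 6-month hearing score, which would be noticeable in a cohort of three. The five-year end point has the same offset: a 60-month post-activation visit would fall outside a limit set at five years from surgery, leaving it unclear which visit provides the final data. If section 7.5 were instead followed from surgery, the 3-month visit could come after very little device use.

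**Working it through.** **Inputs.** Activation at weeks 4-12 after surgery (3.1); visit window of 4 weeks either side (7.5); interims at one and three years and end point at five years (10.7, 10.1). In weeks, 3, 6, 12, 36, 54 and 60 months are 13, 26, 52, 156, 234 and 260.

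**The plan's own figure.** Section 7.5 illustrates its window as 2-4 months for the 3-month visit. With 365.25/12/7 = 4.35 weeks per month, 4 weeks is 0.92 months, so the window is 3 - 0.92 = 2.08 to 3 + 0.92 = 3.92 months. This agrees after rounding.

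**Visits from activation, analyses from surgery.** Visit week = activation week + nominal weeks.

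| Visit | Planned week after surgery | Analysis date | Planned lag | Lag with 4-week window |
|---|---|---|---|---|
| 12 months | 52+4 = 56 to 52+12 = 64 | 52 | 4-12 | 0-16 |
| 36 months | 156+4 = 160 to 156+12 = 168 | 156 | 4-12 | 0-16 |
| 60 months | 260+4 = 264 to 260+12 = 272 | 260 | 4-12 | 0-16 |

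A lag of zero needs activation at week 4 and a visit the full four weeks early. Letting the window also move activation (weeks 0-16) would widen the lag to between -4 and +20 weeks. That is hard to square with the 4-12 weeks of healing in 3.1.

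**What is available at the one-year date.** The 6-month visit is planned at 26+4 = 30 to 26+12 = 38 weeks, and is done by week 42 with the window. Every affected subject therefore has that score.

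**How many subjects are affected.** This depends on a rule the plan does not state:

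- Interim uses the nominal 12-month visit: none.
- Hard cut at each subject's own week 52: on planned dates all 3, 5 or 8 lack the score.
- Hard cut 52 weeks after the last cohort member's surgery: a subject operated *j* x *s* weeks earlier, with activation delay *d*, lacks the score if *d* > *j* x *s*. Surgery spacing *s* is an assumption. For *s* of 12 weeks or more, one subject is missing; for *s* = 8, one (*d* = 4) or two (*d* = 12); for *s* = 4, one, two or three (*d* = 4, 8, 12).

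**Five years.** If *biannual* means six-monthly, the 54-month visit is planned at 234+4 = 238 to 234+12 = 246 weeks, which is 14-22 weeks before week 260. If it means every two years, the last visit planned inside the limit is at 36 months, 260-168 = 92 to 260-160 = 100 weeks before.

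**Everything from surgery.** The planned offset at one and three years is zero. Device use is 13-12 = 1 to 13-4 = 9 weeks at the 3-month visit, 26-12 = 14 to 26-4 = 22 weeks at 6 months, and 52-12 = 40 to 52-4 = 48 weeks at 12 months. The 8-week spread is no wider than the visit window already permits.

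**Which reading applies.** Section 3.1 itself calls activation-timed visits post-operative, so that label in 7.5 does not make surgery the origin. If the same loose usage carries into 10.7, the one-year interim simply means the 12-month visit. If surgery is the origin in both places, the dates coincide as well. The 4-12 week gap arises only when the term is loose in 7.5 and strict in 10.7.

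**The case for a change.** The strongest counter-argument concerns five years. Sections 10.1 and 10.3 clearly count that limit from surgery, so the mixed reading is not contrived there, and it lends some support to a strict reading of 10.7 too. No section names the visit that supplies five-year data, and section 10.2 says there are no secondary endpoints to fall back on. Even an unseen grid that fixed the visit origin would leave the visit-to-analysis link unstated.

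The textual part of this stands: 3.1 and 7.5 are worded differently, and neither 10.1 nor 10.7 names a visit. The consequence does not follow. Section 10.1 uses its endpoint language for a length of follow-up, and 3.1 puts activation-counted visits and a surgery-counted limit in the same heading. Section 10.5 analyses each subject individually, with descriptive statistics and non-parametric tests, and ties no test to a particular five-year visit. An analyst would report the last visit completed and label it with its timing.

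For the interims, 10.7 attaches no efficacy rule; its only stated action concerns safety. Safety is also covered independently of visit labels: "A research assistant will regularly review safety measures every month for all study participants" (section 8.1).

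**Conclusion.** The timing arithmetic is right: with visits counted from activation and analyses from surgery, the 12-, 36- and 60-month visits are planned 4-12 weeks late, or 0-16 weeks with the window. The claimed loss of hearing scores does not follow from the text. It needs one term read two ways, a hard data cut-off, and in the per-cohort case an assumed surgery spacing. With nominal visits, the natural choice for an analyst, no subject lacks an interim score. Under a hard cut, an affected subject still has the 6-month score at one year and the later visit still takes place.

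What remains is a difference in wording between 3.1 and 7.5 and an unnamed visit in 10.1 and 10.7. Aligning them would tidy the text but would alter no efficacy decision, safety action or conclusion, so no change is called for. This judgement assumes that interim results feed no efficacy decision, as 10.7 indicates, and that scores are reported with the visit at which they were obtained.

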7.6 Unscheduled Visits

Unscheduled visits will be taken in the Otology clinic as needed to address any concerns study participants may have regarding the use of their Nucleus ABI24 system541 device.

7.7 Early Termination

Subjects whose participation in the study is terminated early will be replaced through the recruitment of additional subjects through Otology clinic. All subjects may voluntarily withdraw from the study at any time.

7.8 Schedule of Activities (Study Table)

Please see the study grid included in the IRB application.

8. SAFETY AND EFFECTIVENESS ASSESSMENTS

8.1 Safety Assessments

Safety assessments will include complications questionnaires and frequent post-operative follow-up visits. Inquiries about both major and minor complications will be made and any complications will be recorded. A research assistant will regularly review safety measures every month for all study participants and discuss any safety concerns/adverse outcomes with the investigator.

Any reported safety issues will be carefully recorded and following completion of the study, safety outcomes will be analyzed. Any unanticipated adverse events will be reported to the HSC, FDA, and Cochlear Americas (see Section 9).

8.2 Effectiveness Assessments

Effectiveness assessments will be completed based on audiologic testing and subjective questionnaires at each follow-up appointment. These will be compared to the subjects pre-operative baseline measures. In particular, primary dependent measures will include:

- Speech Perception and Lip-reading Enhancement Measures
 1. Monosyllable/Trochee/Spondee Test (MTS), presented via live voice
 2. CUNY Sentences, presented via video laserdisc in the sound-alone, vision alone, and sound-plus vision conditions

- Detection Measures
 3. Aided (ABI) Sound Field Thresholds measured at octave intervals from 250 to 6000 Hz inclusively.

- Psychophysical Measures
 4. Electrical Thresholds Measured in Current Level
 5. Electrical Maximum Comfort Levels Measure in Current Level
 6. Pitch scaling

- Subjective Questionnaires
 7. Hearing Handicap Inventory
 8. Dizziness Handicap Inventory
 9. Quality of Life (SF-36) questionnaire

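### CUNY sound-plus-vision is compared with the pre-operative baseline, and no stated analysis uses the vision-alone score from the same visits

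*Combined protocol and SAP*

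**What the plan says.** Section 8.2 bases effectiveness on audiologic tests and questionnaires at each follow-up and then names the comparator: "These will be compared to the subjects pre-operative baseline measures". Its primary dependent measures include, under a heading that refers to lip-reading enhancement, "Monosyllable/Trochee/Spondee Test (MTS), presented via live voice" and "CUNY Sentences, presented via video laserdisc in the sound-alone, vision alone, and sound-plus vision conditions".

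Section 3.1 schedules "Speech perception and lip-reading enhancement measures at each post-activation interval" for the visits it heads "Three, Six, and Twelve Months, and Biannual Post-activation Visits (for five years following ABI surgery", and lists the same measures at initial activation. Section 7.5 repeats the schedule and adds a window: "Timing of these appointments may vary by as much as four weeks prior to or after the planned follow-up date".

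Section 7.2 puts all baseline procedures at screening. It names three questionnaires and "audiologic tests such as standard audiometric threshold and Auditory Evoked Potential testing". It does not name CUNY, but the wording leaves the list open.

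On control, section 3.1 describes "A single subject research design in which each subject will serve as his or her own control" and rules out masking; section 3.2 confirms that there are no arms. Section 10.5 analyses each subject individually, with descriptive statistics and unnamed non-parametric tests at the 0.05 level. It adds comparisons with earlier cochlear implant performance in the same ear, where such data exist, and with previous NF2 results. Neither uses two conditions measured at the same visit.

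**The concern.** The sound-plus-vision score depends on what the subject hears and on how well the subject lip-reads. Over five years of repeated testing, lip-reading skill and familiarity with the test may both improve whatever the device does. A comparison with a single earlier time point attributes all such change to the same source. With no concurrent control and no masking, nothing else in the stated analysis would reveal the difference.

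The vision-alone condition addresses this directly, since it is the same test, at the same visit, without the sound. The plan collects it but does not say how it enters the analysis. At stake is whether a rise on one of the primary speech measures can be read as benefit from the implant.

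**Working it through.** **1. The plan's own figure.** There is none to reproduce. The documents give no number of test sessions, no practice gain and no standard deviation for CUNY.

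**2. Number of post-operative CUNY sessions** (sections 3.1 and 7.5).
- Biannual as twice a year: months 0, 3, 6 and 12 after activation, then 18, 24, 30, 36, 42, 48, 54 and 60. That is 4 + 8 = 12.
- With a strict stop at five years from surgery: activation comes 4 to 12 weeks after surgery, so the month-60 visit falls outside, leaving 11. The four-week window brings it back only if activation is at week 4.
- Biannual as every two years: months 0, 3, 6, 12, 36 and 60, which is 6.

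**3. What each comparison estimates.** At visit t, let D be the implant's contribution to sound-plus-vision, P the practice gain in sound-plus-vision since baseline, and Q the practice gain in vision-alone since baseline.
- Change from baseline in sound-plus-vision = D + P.
- Same-visit sound-plus-vision minus vision-alone = D + (P − Q), plus whatever sound added before implantation. Section 4.1 requires thresholds of 90 dB or worse and speech recognition of at most 30% in both ears, so that last term is taken here as small. This is an assumption.

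If P = Q, practice cancels in the second comparison. It never cancels in the first.

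**4. Size on the score scale (assumed gains).** With a linear gain of r points per session, the k-th post-operative session carries r × k points of practice.

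| r | k = 6 | k = 11 | k = 12 |
|---|---|---|---|
| 0.5 | 3 | 5.5 | 6 |
| 1 | 6 | 11 | 12 |
| 2 | 12 | 22 | 24 |

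**5. Consequence for the per-subject analysis in 10.5.** The test is unnamed, so take two simple ones, two-sided. A rank test of one baseline score against k later scores has a smallest possible p of 2/(k + 1). A sign test on k same-visit differences has a smallest possible p of 2 × (1/2)^k.

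| k | one baseline against k sessions | k same-visit differences |
|---|---|---|
| 6 | 0.286 | 0.031 |
| 11 | 0.167 | 0.0010 |
| 12 | 0.154 | 0.0005 |

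With a single baseline, that rank test cannot reach 0.05 in any one subject. The sign test can, although it treats a subject's sessions as independent.

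**6. Group-level illustration (not the planned analysis).** Suppose there is no implant effect and the practice gain is g, in standard deviations of the change score. A Wilcoxon signed-rank test at two-sided 5% (4000 simulated trials) rejects this often on change from baseline:

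| g | n = 10 | n = 15 |
|---|---|---|
| 0 | 0.043 | 0.052 |
| 0.25 | 0.106 | 0.138 |
| 0.5 | 0.278 | 0.422 |
| 0.75 | 0.544 | 0.746 |
| 1.0 | 0.784 | 0.932 |

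The same-visit difference stays between 0.04 and 0.06 throughout. That follows by construction, because equal practice was assumed in both conditions.

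**The case against.** The sentence in 8.2 is a general one. It introduces nine measures, and four of them (sound-field thresholds aided by the implant, electrical thresholds, maximum comfort levels and pitch scaling) cannot have a pre-operative value. It therefore cannot be the literal contrast for every item. Section 10.5 neither adopts nor excludes a same-visit contrast. The 8.2 heading refers to lip-reading enhancement, Aim 1 speaks of testing with and without lip-reading cues, and a vision-alone condition has little other evident use. All of this stands. A reader might infer that the plan will count practice as implant benefit, but the documents do not go that far: the contrast is undefined, not shown to be the wrong one. The gap remains because collecting a control condition does not put it into an analysis, and baseline is the comparator that 8.2 states.

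It can also be said that the argument needs a pre-operative CUNY score that 7.2 does not name. A reader might infer that none is taken. That is unsupported too: the list is open, section 4.1 requires speech recognition scores at entry, and section 7.8 refers to a study grid held outside these documents. If no baseline CUNY score is taken, the 8.2 comparison cannot be made for CUNY, and the same-visit contrast matters more.

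Finally, no passage shows that scores rise with practice. That is correct, and every gain used above is an assumption.

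**Conclusion.** The point holds for CUNY sound-plus-vision. Under the only comparator stated in 8.2, improvement from lip-reading or test familiarity cannot be separated from implant benefit, and the condition that would help is collected without a stated analytic role. How much this matters depends on a practice gain that the documents do not give.

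Three wider readings are tempting and not supported:
- **MTS.** It is listed with one live-voice presentation and no same-visit control, so nothing already collected would correct it. Section 8.2 does not say whether the talker is visible.
- **CUNY sound-alone.** Better lip-reading cannot raise it. Only familiarity with the test could act, and vision-alone is not its control.
- **The rejection rates as properties of this trial.** They illustrate a group-level test under assumed gains, whereas 10.5 plans per-subject analysis.

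The conclusion that the same-visit contrast is better rests on practice being about equal in the two conditions and on sound having added little to vision before implantation.

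**What to change.** In 8.2 and 10.5, define the CUNY lip-reading enhancement effect as sound-plus-vision minus vision-alone at the same visit. State that this difference is analysed per subject and followed over visits, name the test, and keep change from baseline as supportive. Say that the contrast removes practice only as far as it is equal in both conditions.

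In 7.2, state whether CUNY is given before surgery and in which conditions. In 3.1 and 7.5, state whether biannual means twice a year or every two years.

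The contrast costs wording only: no new data and no extra test time. Its limitation is that a subject whose vision-alone score is already near the top of the scale has little room to show enhancement, so both component scores should be reported beside the difference.

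A device-off MTS run and a rule against reusing CUNY lists would be additions with their own cost and are not part of this recommendation. Twelve sessions in three conditions make 12 × 3 = 36 post-operative CUNY administrations per subject, and the documents do not say how many lists are available.
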